3.1. Study Population

Subjects (40-90 years old) with Chronic Critical Limb Ischemia who have:

Severe ischemic pedal rest pain (nocturnal metatarsalgia, Rutherford 4) in the index lower limb with ankle and/or toe systolic pressures of less than 50 and 30 mmHg, respectively, classical features of rest pain and on opioids for pain relief. Classical features include pedal pain that is severe and typically occurs at night when the limb is no longer in a dependent position but in severe cases can be continuous. The pain is localized in the distal part of the foot. Partial relief may be obtained by the dependent position whereas cold and elevation of the lower limb aggravates the pain. Severe pain responds only to opioids.

OR

Ischemic ulcers /gangrene (Rutherford 5) in the affected lower limb with ischemic ulcer measurements ≤ 20 cm² in area (≤ 10 cm² for ischemic ulcers at the heel) for the largest ischemic ulcer with or without rest pain, and ankle and/or toe pressures less than 70 and 50 mmHg, respectively.

IN ADDITION, SUBJECTS WILL HAVE:

No option for revascularization by endovascular intervention or bypass surgery (see definitions below).

No option is defined as the inability to receive an endovascular intervention or surgical bypass procedure due to inflow, conduit or outflow reasons or due to a severe and irreversible co-morbidity.

OR

Poor option (high risk) for revascularization by surgery (see definition below) but no option for revascularization by an endovascular procedure (Type D lesions or worse using the TASC II classification).¹

Definition for poor option (high risk) for revascularization surgery:

Anatomic

- Need for a tibial level synthetic or cryopreserved bypass
- Need for use of great saphenous vein < 3 mm in diameter for tibial level bypass based on venous duplex ultrasound
- Need for use of spliced vein or single piece of non-great saphenous vein < 3 mm in diameter, for tibial level bypass
- Distal target unsuitable for bypass, e.g. < 2 mm in diameter or circumferentially calcified

¹Norgren, L., Hiatt, W.R., et al., Inter-Society Consensus for the Management of Peripheral Arterial Disease (TASC II), Eur J. VascEndovascSurg, Vol 33, S1-S70; 2007.

- Open lower extremity wound that would preclude construction of bypass

OR

Medical

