9. EVALUATIONS AND STATISTICAL METHODS

9.1. Evaluations

The following evaluations relating to tolerability, safety and clinical benefit will be made:

1. Adverse events (AEs) suspected to be related to injections of HGF plasmid
2. Discontinuations related to adverse effects from the injections of HGF plasmid
3. All AEs up to Month 3, Month 6, Month 12, and Month 18
4. Serious adverse events (SAEs) up to Month 3, Month 6, Month 12, and Month 18
5. Number of deaths and cause over the 18 month period up to Month 3, Month 6, Month 12, and Month 18
6. Number of subjects in whom the largest ulcer healed completely or gets smaller (photo confirmation) at 6, 12 and 18 months (cumulative)
7. Number of subjects in whom rest pain (based on the 100 mm VAS scale) reduces by 20 mm or more or was completely relieved at 6, 12 and 18 months (cumulative)
8. Change in VascuQol Questionnaire (QOL) score compared to the baseline at 6, 12 and 18 months
9. Number of subjects revascularized (bypass or endovascular intervention) up to Month 3, Month 6, Month 12, and Month 18
10. Number of subjects with minor and number of subjects with major amputations (at or above the ankle) up to Month 3, Month 6, Month 12, and Month 18

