9.2.2. Statistical Analysis for Efficacy and Safety

Categorical data will be summarized by the use of frequency tables showing the number and percentage of subjects falling within a particular category by visit, and detailed line listings of subjects will be provided.

Continuous data will be summarized by reporting number of observations, mean, standard deviation (SD), median, minimum and maximum by visit. Summary statistics will be provided for baseline and the change (with percent change) from baseline. A one-sample t-test will be performed on within group change-from-baseline for individual time point (Months 6, 9, 12, 15, and 18 with last observation data (assessed prior to intervention or worse score for deaths) carry-forward (LOCF)).

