This statistical analysis plan (SAP) provides a comprehensive and detailed description of strategy, rationale, and statistical methods to be used to assess clinical efficacy and safety. The purpose of the SAP is to ensure the credibility of the study findings in the pre-specified statistical approaches to the analysis of study data prior to the database lock. This SAP provides additional details concerning the statistical analysis outlined in the protocol.

2 Investigational Plan

A phase 3 study AG-CLI-0206 was planned as a registration study and received Special Protocol Assessment (SPA) approval by the U.S. Food and Drug Administration (FDA). Prior to undertaking the phase 3 study, a pilot study will confirm the feasibility of the study-related activities in study AG-CLI-0206 and the tolerability of the dosage regimen of AMG0001.

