2.4 Statistical and Analytical Procedures

2.4.1 General Statistical Considerations

This study is not powered for statistical inference, and any testing will be considered descriptive and exploratory. All data summarized in tabular form will have accompanying listings. Figures may also be provided.

Unless otherwise noted, the term “descriptive statistics” will refer to frequency and percent (%) for categorical data and number of observations (n), mean, standard deviation (SD), median, minimum, and maximum for continuous data.

Biodata (serum HGF protein) values reported as below the level of quantitation (10 copies/ uL) will be reported as BLQ and excluded in calculation of the mean and SD.

All analyses will be conducted using SAS 9.4 or later.

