2.5 Statistical Methods

2.5.1 Study Population

A single study population will be used for all efficacy and safety analyses, that is, the modified Intent-To-Treat population (mITT) population. The population is defined as all subjects who received at least one injection of study treatment.

2.5.2 Disposition, Demographics, Protocol Deviations, and Background Characteristics (Including Medical History)

The number of subjects enrolled (i.e. those who received at least one injection of study treatment) and subjects who completed the study or prematurely discontinued with the primary reason for study discontinuation, completion of the Month 18 clinic visit, and completion of the Month 36 LTFU questionnaire will be summarized.

A table showing number of subjects in the study will be tabulated at Day 0, month 3, month 6, month 9, month 12, month 15, month 18, LTFU (24 month, 30 months, 36 months).

A major protocol deviation is defined as any divergence from the protocol that could have a significant effect on the subject's safety, rights, or welfare and/or on the integrity of the study data, i.e., non-adherence on the part of the subject, the investigator, or the sponsor to protocol-specific inclusion/exclusion criteria, primary objective variable criteria, and/or Good Clinical Practice (GCP) guideline. A minor protocol deviation is defined as either any deviation from the protocol that does not have a significant effect on the participant's safety, rights or welfare, and / or the integrity of the study data or as defined in the protocol or any non-adherence to protocol-specific study procedures or schedules that does not involve inclusion/exclusion criteria, primary objective variable criteria, and/or GCP guidelines and do not impact the study. A listing of subjects with major protocol violations will be provided together with a description of the criteria in the footnotes.

The following demographics, baseline characteristics, and Disease History at baseline will be reported.

- Demographics: age in years, age group (≤ 79 years, > 80 years), sex, race, height, weight, ethnicity
- Baseline characteristics: past tobacco use, current tobacco use, alcohol use, mobility, self-care, anxiety/depression

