2.5.5 Efficacy Analysis

- Ulcer improvement**

A table showing the number of subjects completely healed in the target ulcer will be provided at up to 6 months, > 6 months to 12 months, from >12 months to 18 months. If available, the number of subjects with at least 20% reduction in bi-dimensional size (by measuring largest diameters) will be provided. The reduction in bi-dimensional size will be calculated by taking the product of the largest diameters for each baseline and postbaseline measurement, then subtracting the baseline result from the postbaseline result.

- Ischemic Rest pain (of the index leg) using a 10 cm VAS scale**

Rest pain severity will be assessed at the specified predetermined time points. Rest pain severity will also be assessed prior to surgical revascularization or major amputation (of the index leg). A table showing the number of subjects reduced by ≥ 20 mm from baseline in VAS score will be provided at up to 6 months, > 6 months to 12 months, from >12 months to 18 months. Summary statistics will be provided for baseline and change from baseline for each visit and LOCF. One sample t-test for change-from-baseline will be performed. If death occurs, the worst score prior to death instead of last observation will be carried forward.

- Hemodynamic Measurements**

Summary statistics will be provided for baseline and change from baseline for hemodynamic parameters (right/left brachial systolic pressure, ankle systolic pressure measured at dorsalis pedis and posterior tibial, toe systolic pressure, calculated ABI, and calculated TBI) by visit. At each visit, only subjects who have a non-missing value at both baseline and the specific visit will be summarized. Two-sided one-sample t-test will be performed for each visit and LOCF.

- Subjects with any worsening CLI event of index leg**

A summary table and listing of worsening CLI-related events of the index leg including any new or worsening events, worsening rest pain, new ulcer or worsening ulcer, new or worsening wound infection, peripheral vascular intervention, complication of a peripheral vascular intervention, cellulitis, and amputation due to worsening CLI will be provided.

- Subjects who either died, had MI, Stroke, revascularization (by surgical bypass, by endovascular intervention, by hybrid procedure), major amputation, or all-cause death**

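### SAP 2.5.5 sets a 20% threshold for ulcer shrinkage but defines the reduction as an undivided difference, post-baseline minus baseline, which cannot be compared with a percentage and is negative when the ulcer shrinks

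*SAP*

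**What the plan says.** Under Ulcer improvement, SAP 2.5.5 first plans a table of subjects whose target ulcer has healed completely, for three periods up to Month 18. It then adds, if the data are available, that "the number of subjects with at least 20% reduction in bi-dimensional size (by measuring largest diameters) will be provided". The next sentence gives the calculation: form the product of the largest diameters at baseline and at the post-baseline assessment, "then subtracting the baseline result from the postbaseline result". It contains no division, no factor of 100 and no reversal of sign.

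No other section supplies a percent formula for this count.

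- Protocol 9.1, item 6, counts subjects whose largest ulcer is fully healed or smaller, confirmed by photograph. It has no 20% threshold and no formula.
- Protocol 9.2.2 says of continuous data in general: "Summary statistics will be provided for baseline and the change (with percent change) from baseline". It does not define an ulcer responder.

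**The concern.** Two consecutive SAP sentences do not fit together. The first sets a relative threshold. The second defines the quantity to be tested as an absolute difference, in the direction that makes shrinkage negative. The rest-pain item in the same section pairs a threshold in millimetres with a change in VAS score, so an absolute difference suits it. The ulcer item carries an absolute difference over to a percentage threshold, where it does not fit.

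The SAP introduction states: "The purpose of the SAP is to ensure the credibility of the study findings in the pre-specified statistical approaches". Here the pre-specified calculation cannot yield the pre-specified count. Whoever programs a sensible table must depart from the text without a written rule, and two programmers could depart from it differently. In a study of 8-10 subjects, each subject classified differently moves the count by one.

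**Working it through.** The plan gives no figure for this endpoint, so there is nothing to reproduce. The check applies the SAP rule to assumed ulcer sizes and compares it with percent reduction.

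Inputs:
- threshold of 20% or more, SAP 2.5.5;
- size = product of the largest diameters, SAP 2.5.5;
- the baseline and post-baseline products below, which are assumed for illustration (any squared unit).

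Formulas, with B the baseline product and P the post-baseline product:
- SAP value: P - B
- percent change: 100 x (P - B) / B
- percent reduction: 100 x (B - P) / B

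| B to P | SAP value | Percent change | Percent reduction | 20% or more? |
|---|---|---|---|---|
| 10 to 7 | -3 | -30% | 30% | yes |
| 2 to 3 | +1 | +50% | -50% | no |
| 20 to 17.5 | -2.5 | -12.5% | 12.5% | no |
| 2 to 1 | -1 | -50% | 50% | yes |
| 10 to 0 (healed) | -10 | -100% | 100% | yes |

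Step 1, the rule as written. Every shrinking ulcer has a negative SAP value and the growing one a positive value. The values are in squared length: changing from cm to mm multiplies each by 100 (-3 becomes -300) and leaves the percentages unchanged. A number that depends on the unit cannot be compared with 20%.

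Step 2, reverse the sign but do not divide. The ulcer going from 20 to 17.5 scores 2.5 and is not a responder. The one going from 2 to 1 scores 1 and is a responder. Any cutoff low enough to count the second also counts the first, so no single cutoff on the undivided difference classifies both correctly. The reason is that 20% of baseline is 0.2 x 20 = 4 for the first ulcer and 0.2 x 2 = 0.4 for the second.

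Step 3, divide by baseline but keep the SAP's direction. This is ordinary percent change. With the cutoff written as -20% or lower, all five rows are classified correctly. With the cutoff left as +20% or higher, only the growing ulcer would count.

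Step 4, percent reduction with a cutoff of 20% or higher gives the same classification as percent change of -20% or lower.

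So division by baseline is indispensable. The direction of subtraction is free, provided the threshold is written to match.

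**The case against.** The best defence is that the intent is plain. The 20% already fixes a relative scale. Subtracting baseline from the later value is the usual direction for change from baseline, the quantity this section summarises for other endpoints. Protocol 9.2.2 names percent change. On this view the sentence is loosely worded, and a competent programmer would divide by baseline and look for -20% or lower.

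Much of this stands. The sign alone is not a separate fatal error: step 3 shows that the stated direction works once the value is divided and the cutoff is signed to match. A reader might infer that both the direction and the division must be changed before the count can be right; the arithmetic does not support that. A reader might also infer that the analysis will report growing ulcers as responders. That would require someone to set an undivided or wrongly signed value against a cutoff that the SAP does not state in that form, and the documents do not say this will be done.

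The count may also never be produced. It is conditional on availability. Protocol 4.9 describes tracings at Screening and Day 0 and photographs afterwards, and Protocol Table 3 marks tracings at Day 0 only.

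What does not stand is the claim that nothing needs correcting. The sentence states a specific calculation, and that calculation does not give a percentage. A general remark about summaries of continuous data does not replace it.

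**Conclusion.** The point holds as a definition error of small consequence. Followed literally, SAP 2.5.5 cannot produce its 20% count, because the defined quantity is not divided by baseline. Its sign also disagrees with the word reduction, which must be settled together with the threshold.

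The effect is confined to one descriptive efficacy count, given only if available, in about 8-10 subjects. No misclassification rate can be stated, because the documents do not say how many subjects will have an ulcer. The separate count of complete healing, the protocol's evaluation of ulcers healed or smaller, and the primary objectives of feasibility, tolerability and safety do not use this formula. A reader might infer that the trial's efficacy findings as a whole are in doubt; the documents do not support that. SAP 2.4.1 also says "All data summarized in tabular form will have accompanying listings", so a reader who noticed the problem could recalculate the count if the listing carries the diameters.

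The ulcer sizes used here are assumed, but the conclusion does not depend on them: an undivided difference carries units whatever the ulcer's size or shape.

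**What to change.** Replace the last sentence of the ulcer item in SAP 2.5.5 with: percent reduction = 100 x (baseline product - post-baseline product) / baseline product; responder if 20% or more. Equivalently, define percent change from baseline and count subjects at -20% or lower. Either form is sufficient; use one throughout.

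The cost is one sentence. The correction itself calls for no measurement beyond those the count already presupposes.

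Two additions are optional and not part of the error. One is to state whether a completely healed ulcer (product 0, a 100% reduction) also enters the 20% count. The other is to show beside the count how many subjects had a baseline target ulcer and a later size assessment. SAP 2.5.1 says "A single study population will be used for all efficacy and safety analyses", namely all injected subjects, and Protocol 3.1 also admits subjects on the basis of rest pain (Rutherford 4), so some may have no ulcer to measure.

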4.4. Concomitant Medications

Concomitant medication and the indication for its use must be clearly documented and recorded in the source documentation and CRF for each subject. Any medications taken from the date informed consent is signed and onward should be documented in the CRF.

The use of analgesic medications during the study should be carefully recorded. Investigators should refrain from making changes in the subject's use of analgesic medications after the baseline visit, unless the subject's medical condition warrants changes to their treatment. Changes in the use of analgesic medications after the baseline visit could confound the interpretation of endpoint assessments.

Topical wound medications must be captured as concomitant medications in the CRFs. **Wound care products such as Regranex® (rhPDGF), Apligraft®, Dermagraft®, Oasis®, as well as any other skin equivalents or topical growth factors are excluded for use during this trial. Hyperbaric oxygen (HBO) treatment is also excluded.**

All subjects should be on a statin and an anti-platelet agent (e.g., clopidogrel, ticlopidine, aspirin, etc.) as part of their standard of care, unless contraindicated. Subjects for which these agents are contraindicated must have the restriction reason recorded in their source documentation and CRF.

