4.11. Ischemic Rest Pain Measurement

The severity of rest pain based on the average over the previous 7 days will be recorded using the 10 cm visual analog scale (VAS) (see Appendix E). The VAS score must be documented at all visits and prior to any planned intervention (revascularization or major amputation). In order to assess rest pain adequately, the use of pain medication/opioids must be specifically documented in the CRF during the VAS evaluation period. The subject should not be allowed to see his previous rest pain measurements nor should the score be revealed to him/her.

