5.2. Confirmation of Subjects' CLI Stability Pre-Dose

Sites must perform an assessment of the subject's CLI status in order to confirm stability prior to dosing. The stability assessment should occur on Day 0 prior to dosing (≥ 2 weeks between the screening and the Day 0 assessments), and should include ulcer and leg photography and tracings of the largest ulcer on the index leg (with ulcer debridement, if necessary, occurring prior to photography and tracing), hemodynamic measurements, and measurement of ischemic rest pain

severity. The assessment will confirm that the ulcer(s) and gangrene have not increased in size excessively so that the subject requires a surgical intervention or decreased in size excessively so that the subject's lesions will heal spontaneously without study product. The assessment will also confirm that hemodynamic measurements have not changed markedly ($\pm > 0.1$ ABI or TBI) and the ischemic rest pain has not increased or decreased greatly despite continuing the same dose of analgesics. Subjects with unstable CLI will not be randomized. They will be considered screen failures. The entry committee will verify the CLI stability post-randomization

5.3. Dosing Visit Study Procedures: Day 0

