2.4.2 Missing Data

For endpoints involving the VascuQoL assessment, non-missing data after revascularization or major amputation will be included in analysis, and missing values for subjects who are dead at the time point of interest will be scored as 0.

For the Visual Analogue Scale (VAS), each subject’s data after revascularization or major amputation will be imputed using the value of the last available assessment prior to intervention, and the worst score available will be imputed for assessments after death.

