2.5.4 Concomitant Medication

Concomitant medications are medications which started prior to, on, or after the first dose of study medication and taken concomitantly during the treatment period. Concomitant medications will be coded using WHO Drug dictionary version September 2013.

The following concomitant medication listings will be provided: all, medications with indications for MI, stroke, pain, hypertension, and hyperlipidemia by treatment. A listing for subject secondary prevention status at baseline will be provided.

Medications reported as being taken at Screening and Day 0 along with concomitant medications will be summarized by Anatomical Therapeutic Chemical (ATC) classification level 4 description and preferred name.

In addition, the use of statin and anti-platelet agents at screening will be summarized and listed.

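### The ≥20 mm rest-pain count and the VAS t-test take no account of post-baseline analgesic changes, which the protocol names as a possible confounder and requires to be recorded

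*SAP*

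**What the plan says.** **The endpoint.** For rest pain, SAP 2.5.5 states: "A table showing the number of subjects reduced by ≥ 20 mm from baseline in VAS score will be provided". It adds summary statistics for VAS change and says: "One sample t-test for change-from-baseline will be performed". Protocol 9.1 has the corresponding item: "Number of subjects in whom rest pain (based on the 100 mm VAS scale) reduces by 20 mm or more or was completely relieved". None of these carries a condition on analgesic use.

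**Events the SAP does handle.** For the VAS, SAP 2.4.2 says "each subject’s data after revascularization or major amputation will be imputed using the value of the last available assessment prior to intervention", and it imputes a worst score after death. Analgesic change has no rule there.

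**What the protocol says about analgesics.**
- Section 3.1: Rutherford 4 subjects enter already taking opioids.
- Section 4.4: investigators should avoid changing analgesics after baseline but may do so when the subject's condition calls for it. The reason given is: "Changes in the use of analgesic medications after the baseline visit could confound the interpretation of endpoint assessments".
- Section 4.11: so that rest pain can be properly assessed, "the use of pain medication/opioids must be specifically documented in the CRF during the VAS evaluation period".
- Section 5.2: before the first dose, pain stability is judged "despite continuing the same dose of analgesics".

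**Where pain drugs are reported.** SAP 2.5.4 plans a listing of drugs with a pain indication and a summary of concomitant medications by ATC level 4 and preferred name. Protocol 9.2.1 plans a summary of pain medications.

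**The concern.** The protocol reads pain against analgesic use at entry and requires the data for doing so afterwards. The analysis then leaves that link out. If a subject's opioid dose goes up and the 7-day average pain drops by 20 mm, the subject enters the efficacy count on the same footing as one whose pain dropped on unchanged analgesics. Conversely, a subject who cuts down opioids with pain unchanged shows no benefit.

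The study has one open-label arm (SAP 2.2), so no comparison group would show how much of the fall goes with analgesic changes. What is at stake is how a small efficacy count from a pilot is read ahead of the phase 3 study. Patient safety and the primary objectives are not affected.

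**Working it through.** The plan states no power, alpha or expected responder rate for this endpoint, so there is no figure of its own to reproduce. The check compares the texts and then works out how much one subject weighs.

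**Step 1. Is there any analgesic condition on the VAS analysis?**

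| Place | Subject | Analgesic condition |
|---|---|---|
| Protocol 9.1 | Fall of 20 mm or complete relief | None |
| Protocol 9.2.2 | One-sample t-test on change | None |
| SAP 2.5.5 | Fall of 20 mm; t-test on change | None |
| SAP 2.4.2 | VAS data rules | Revascularization, major amputation and death only |
| SAP 2.5.4, Protocol 9.2.1 | Pain drugs listed and summarised | Not tied to VAS or to visit |
| Protocol 5.2 | Stability of pain before Day 0 | Same analgesic dose |

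Only the entry check conditions on analgesics. No section defines an analgesic increase or plans a sensitivity analysis or cross-listing against VAS.

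**Step 2. Weight of one subject.** Input: about 8–10 subjects (SAP 2.2), all treated subjects in the denominator (SAP 2.5.1).
- Rate: 100/n, so 100/10 = 10 points and 100/8 = 12.5 points. Two subjects: 20 or 25 points.
- Mean change if one subject falls by exactly 20 mm: 20/n, so 20/10 = 2.0 mm and 20/8 = 2.5 mm.

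**Step 3. How often could it happen?** The documents give no value. Assume a chance q per subject of a 20 mm fall that accompanies an analgesic increase. The chance of at least one is 1 − (1 − q)^n.

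| q (assumed) | n=8 | n=10 |
|---|---|---|
| 0.10 | 0.57 | 0.65 |
| 0.20 | 0.83 | 0.89 |
| 0.30 | 0.94 | 0.97 |

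These figures show only what each assumed q would imply. They are not an estimate for this trial.

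**Step 4. The t-test.** Assume no treatment effect, an SD of change of 15–30 mm (not in the documents), and that k subjects fall 20 mm. Approximate this by shifting the mean by 20k/n with the SD held fixed. A two-sided 5% test then rejects with probability 0.054–0.070 for k=1 and 0.088–0.232 for k=3, across n=8 and n=10. One subject hardly affects the test; the count is the more sensitive output.

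**The case against.** The case on the other side is substantial, and several parts of it stand.

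- **The pain-drug data are used.** A reader might infer that the SAP ignores them or merely lists them. It does neither: it also summarises concomitant medications. With 8–10 subjects, someone could cross-read the listings by hand. What is missing is a pre-specified link.
- **Worsening is not hidden.** A reader might infer that deteriorating subjects given more opioids vanish into the successes. SAP 2.5.5 plans a separate table and listing of index-leg worsening that includes rest pain. Such a subject would also have to end at least 20 mm below the original baseline, not just below the worsened level.
- **The study is exploratory.** The primary objectives are feasibility, tolerability and safety, and SAP 2.4.1 disclaims inference. The SAP reports a number of subjects reduced and does not call them responders to AMG0001. This limits the weight of the point. Still, the result appears under efficacy with a test attached.
- **Analgesic data cannot isolate the product's effect.** This is correct: a single open-label arm also leaves natural course, expectation and regression to the mean. The split removes one ambiguity only.
- **Analgesics before the VAS are barred (Protocol 3.4).** That rule concerns dosing visits. The VAS is a 7-day average (Protocol 4.11, Appendix E), so a change in maintenance opioids still enters it.
- **The concomitant-medication definition.** SAP 2.5.4 covers drugs "taken concomitantly during the treatment period". A reader might infer that analgesics started after the last dose are lost while VAS is still read at Months 15 and 18. The SAP does not define that period, promises a listing of all concomitant medications, and the protocol reviews medication through Month 18. This is a separate minor clarification and no part of the present point.

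**Conclusion.** The point holds as a matter of text. The ≥20 mm count and the VAS t-test are blind to analgesic changes that the protocol itself calls a possible confounder and requires to be recorded. Each subject whose fall accompanies an increase moves the rate by 10 points (n=10) or 12.5 points (n=8). If the denominator were restricted to subjects with rest pain at baseline, each would weigh more, because Rutherford 5 subjects may enter without it (Protocol 3.1).

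The documents do not support a claim that any particular number of subjects will be affected, or that the reported rate will be inflated by a known amount. The escalation rate is not given, and the ranges above rest on assumed values. This is an inexpensive improvement to an exploratory analysis, worth making before database lock, because a split chosen after seeing the results would carry less weight.

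**What to change.** In SAP 2.5.5:

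1. Keep the total count of subjects with a ≥20 mm fall and split it into two rows that sum to it: (a) falls with no analgesic increase over baseline in that VAS period, meaning no new opioid or other analgesic and, where the CRF records dose, no higher dose; (b) falls with an increase. State that row (a) is the count read as pain response.
2. Add a by-subject, by-visit listing of VAS beside analgesic use.
3. Keep every VAS reading in the change-from-baseline summary and the t-test, and flag readings taken after an increase.

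Readings after an increase should not be left out. Suppose (assumed) that 3 of 10 subjects escalate and still worsen by 2 cm while 7 improve by 1 cm. With all readings the mean change is (3 × 2 − 7 × 1)/10 = −0.1 cm; dropping the three gives −1.0 cm. The exclusion would favour the product.

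The SAP should also say in advance how it treats opioid switches, as-needed use, analgesics taken for other conditions and missing analgesic records, so that the two rows still sum to the total.

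**Cost.** One derived flag and one listing, with no change to patient care. The pain-response count may be lower. How fine the flag can be depends on the CRF: the protocol requires use to be documented but does not say that dose is captured. If dose is absent, a new-drug flag and the listing are the minimum.
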